3.2. Secondary Endpoints

- Time from study initiation to 48 hours fever-free (<100.5 degrees F orally)
- Duration of hospitalization
- Time in ICU
- Time to ICU admission
- Number of days requiring supplemental oxygen (or supplemental oxygen above baseline levels)
- Total days of mechanical ventilation
- Time to mechanical ventilation
- Shock and need for pressure support

- Incidence of any infection (viral, fungal, bacterial) including opportunistic infections
- Time to clinical resolution
- Grade 3 or higher toxicity
- Viral clearance at the end of therapy
- Time to viral clearance
- Overall survival at 3 and 12 months

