4. BACKGROUND

4.1 SARS-CoV-2 and COVID-19:

The SARS-CoV-2 virus, a novel coronavirus originated from Wuhan China and represents a serious human to human pathogenic virus. SARS-CoV-2 has a variable phenotype ranging from asymptomatic carrier state to rapidly progressive acute respiratory distress syndrome. The clinical syndrome manifested by SARS-CoV-2 is termed COVID-19. Both the infectiveness and pathogenic nature of this respiratory droplet transmitted RNA virus greatly exceeds that of influenza, likely as a consequence of no prior human exposure or available vaccine. SARS-CoV-2 has rapidly spread throughout the world and was recently by the WHO as a pandemic pathogen. Notably, SARS-CoV-2 has common presentation of fever (89%), cough (68%), CT abnormalities (86%) and lymphocytopenia (84%) with nausea (5%) and diarrhea (4%) being uncommon. Severe disease that requires admission occurs in 20% and a subset of these patients require ICU care (6%), intubation (2.3%) or die (1.4%).¹ The death rate from COVID-19 in different populations has been different from China (updated data, 2.4%) to Italy (7.2%).^{2,3} Death rate from COVID-19 increases proportionately with older age, being highest among older patients and also those who are immunocompromised or have other co-morbidities or lymphocytopenia ^{1,3-5}. Among hospitalized cancer patients with COVID-19 in China, a 38% frequency of mechanical ventilation or death occurred compared to 8% among patients without cancer⁶. The systemic and pulmonary pathogenesis derived from clinical cases of ICU hospitalized COVID-19 cases and autopsy series demonstrates increased levels of plasma inflammatory cytokines including TNF-alpha, IL-6, and IL-2, and IL-10 and neutrophilic infiltration, macrophages, monocytes, minimal lymphocytes (CD4+ T-cells predominately) and type 2 pneumocytes with EM viral particles.^{7,8} Other risk factors for severe COVID-19 illness include the presence of neutrophilia, organ dysfunction (elevated LDH), coagulation abnormalities, thrombocytopenia, and lymphocytopenia suggesting both findings observed in hemophagocytic syndrome that often accompanies immune deficiency and dysregulation ^{1,9,10}.

4.2 Immune Response to SARS-CoV-2:

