Design and Sample Size: Based on a study in China, we assume that the event rate is 40% with standard care and that the event rate can be reduced to 15% when Ibrutinib is added to standard care for COVID-19. With 60 patients and using a standard group sequential design, there is 82.8% power to detect a reduction in the event rate under the alternative hypothesis and constraining the one-sided type I error to 20%. Power was calculated using a z-test for the difference in two proportions, pooled variance, and adjustment for small sample sizes with the Casagrande-Pike-Smith correction (EAST v6.5; Cytel, Inc). There will be an interim analysis when 50% of randomized patients have been followed for 30 days from registration. The study will be stopped early if at the interim analysis the observed event rate is higher in the ibrutinib arm (Arm A) than in the control arm (Arm B). We will plan to over-accrue by about 10% for a total accrual goal of 66 patients.

Although the actual reduction in the event rate could be larger than 25%, it could also be as low as 20% and still be quite meaningful. Furthermore, there is uncertainty in the event rate of the control arm. For these reasons, we have incorporated increased flexibility at the time of the interim analysis to potentially increase the sample size if conditional power indicates promising results, and will thus implement an adaptive group sequential design (Chen, DeMets, Lan; 2004).

At the interim analysis, there are 4 possible outcomes: 1) the futility criteria are met and the trial stops early; 2) the conditional power is unfavorable ($<50\%$), and enrollment continues to the planned sample size without an increase in sample size; 3) the conditional power is in a promising zone (defined as conditional power $\geq 50\%$ and $< 82.8\%$), and sample size may be re-estimated with the original sample size updated to boost the power to a target of 82.8%, subject to a maximum sample size of 120; or 4) the conditional power is favorable ($\geq 82.8\%$), and enrollment continues to the planned

sample size without an increase in sample size. When using this procedure, no adjustment to the final test statistic or critical value from the original design is required to control the Type I error rate. In addition, if the conditional power is in the promising zone, we can choose not to increase the sample size beyond what was originally planned or by a flexible amount without penalty.

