We note that the above stopping rules may be adjusted at any time during the conduct of the trial and in consideration of newly acquired information regarding the adverse event profile of the treatment(s) under investigation. The study team may choose to suspend

accrual because of unexpected adverse event profiles that have not met the specified rules above.

Secondary Endpoints: At the final analysis, all adverse events will be summarized by grade, type, and attribution (regardless of attribution and treatment-related) for each arm. Time-to-event endpoints such as time to discharge and overall survival will be estimated for each arm using the method of Kaplan-Meier. Medians estimates and/or estimates at specific time points will be provided with 95% confidence intervals. The proportion of patients with viral clearance at the time of hospital discharge will be estimated with 95% confidence intervals for each arm. For all biomarkers, descriptive statistics (e.g., means, medians, standard deviations, interquartile range) and graphical displays will be used to characterize central tendency and variability over time. Values will be log transformed as appropriate to reflect biologic plausibility. We will evaluate for statistical trends over time among the biologic measurements, with multiple measurements per patient, using mixed effects models. Lastly, associations between baseline characteristics and the primary endpoint will be evaluated with logistic regression, adjusting for arm. These analyses will be largely descriptive, as a result of a limited sample size.

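### Section 13 puts time to mechanical ventilation and time to ICU admission under Kaplan-Meier without treating death as a competing event or saying that discharged patients stay at risk (minor)

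*Combined protocol and SAP*

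**What the plan says.** Section 3.2 lists "Time to mechanical ventilation" and "Time to ICU admission" among the secondary endpoints. The Secondary Endpoints paragraph of Section 13 gives the only method for endpoints of this kind: "Time-to-event endpoints such as time to discharge and overall survival will be estimated for each arm using the method of Kaplan-Meier". It adds medians or time-point estimates with 95% confidence intervals, and describes these analyses as mostly descriptive because the sample is small.

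For these two endpoints the plan gives no time horizon, no censoring rule and no competing event. It does not say what happens to a patient who goes home, or who dies, without having been ventilated or admitted to the ICU.

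Other sections bear on follow-up. Section 7.7 continues follow-up to 12 months, by telephone or video after hospitalization. Section 7.8 removes patients only for death or full withdrawal of consent. The Section 12 calendar schedules a 1-month contact that includes medical history and adverse events.

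**The concern.** Kaplan-Meier needs no special rule for overall survival. Ventilation and ICU admission differ, because a patient can leave the pool of possible events in two other ways.

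- **Death without the event.** The patient can no longer be ventilated. Censoring the death makes Kaplan-Meier treat that patient as if the event could still happen later, so one minus Kaplan-Meier exceeds the proportion who actually have the event.
- **Discharge alive.** This is likely to be the commonest exit. On the design assumption "we assume that the event rate is 40% with standard care and that the event rate can be reduced to 15% when Ibrutinib is added", 60% and 85% of patients have no composite event. If the discharge date were the censoring date, patients who had recovered would be assumed to carry the same later risk as those still in hospital.

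What is at stake is the published per-arm risk of ventilation or ICU admission. Two statisticians could follow Section 13 faithfully and report different figures.

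**Working it through.** **The plan's own figures.** The plan gives no number for these endpoints. The nearest figure is the power for the primary endpoint: "With 60 patients and using a standard group sequential design, there is 82.8% power to detect a reduction in the event rate", with one-sided alpha 0.20. I reproduced it to confirm the rates and sample size used below. With 30 per arm, the Casagrande-Pike-Smith correction leaves an effective n of 22.5 per arm.

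- Null SE (pooled): √(2 × 0.275 × 0.725 / 22.5) = 0.133.
- Alternative SE: √((0.15 × 0.85 + 0.40 × 0.60) / 22.5) = 0.128.
- Fixed-design power: Φ((0.25 − 0.842 × 0.133) / 0.128) = 0.860.
- With the futility look at half the information: 0.8277, against 82.8% stated.

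**Case A: deaths censored, discharged patients kept event-free to day 30.** Assumptions, since the documents give none: ventilated v = 20-25%, dying first d = 5-20%, 33 per arm (half of the accrual goal of 66). The reference SE is √(v(1−v)/33): 7.0 points at v = 20% and 7.5 at 25%, so half an SE is 3.5 to 3.8 points.

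If deaths and ventilations have the same time pattern, 1−KM = 1 − (1−v−d)^(v/(v+d)).

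| v | d | 1−KM | Overstatement | In SE |
|---|---|---|---|---|
| 20% | 5% | 20.6% | 0.6 points | 0.08 |
| 20% | 20% | 22.5% | 2.5 points | 0.36 |
| 25% | 5% | 25.7% | 0.7 points | 0.09 |
| 25% | 20% | 28.3% | 3.3 points | 0.43 |

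The error shrinks when deaths come later than ventilations. Simulation with mean time to ventilation of 2 to 6 days and mean time to death of 6 or 8 days gives about 0.1 to 3.2 points. The arithmetic ceiling is every death preceding every ventilation, where 1−KM = v/(1−d). At the worst corner that is 0.25/0.80 = 31.25%, or 6.25 points (0.83 SE), but that timing is extreme.

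**Case B: patients also censored at discharge.** This is hypothetical. With constant event hazard λ and discharge hazard δ = ln 2 / median stay, and no deaths, the true day-30 risk is λ/(λ+δ) × (1 − exp(−30(λ+δ))), while 1−KM = 1 − exp(−30λ). The planned composite rates serve only as illustrative risks, and the median stays are assumed.

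- True risk 40%, median stay 10 days: δ = 0.0693, λ = 0.0486, 1−KM = 0.767. Overstatement 0.367; with SE √(0.4 × 0.6/30) = 0.089, about 4.1 SE.
- True risk 15%, median stay 7 days: δ = 0.0990, λ = 0.0181, 1−KM = 0.419. Overstatement 0.269; with SE 0.065, about 4.1 SE.

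The size depends on timing:

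- Constant hazards, risks of 10-40%, median stays of 5-21 days: 1.0 to 6.4 SE.
- Event hazard falling over time (time constant 2-10 days), median stays of 7-12 days: 0.02 to 2.9 SE.
- 20-25% ventilated, 5-20% dying first, log-normal stay with median 8 days: about 2-3 points when ventilation occurs at a mean of 2 days and few die first, rising to more than 4 SE at a mean of 6 days.

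**Arm comparison under Case B (constant hazards).**

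| Setting | Median stay, control / ibrutinib | True difference | 1−KM difference |
|---|---|---|---|
| Equal event hazards | 10 / 7 days | 0.400 − 0.325 = 0.075 | 0.767 − 0.767 = 0 |
| 40% vs 15% | 10 / 7 days | 0.25 | 0.348 |
| 40% vs 15% | 14 / 7 days | 0.25 | 0.257 |
| 40% vs 15% | 14 / 5 days | 0.25 | 0.153 |

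The contrast can be hidden, inflated, nearly unchanged or shrunk.

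**The case against.** The strongest reply is that nothing in the documents censors at discharge. Sections 7.7 and 7.8 keep discharged patients under observation, and the calendar has a 1-month contact, so a statistician could reasonably keep them at risk. The scheduled vital signs do stop at end of treatment, but that is a fixed day (day 14, plus up to 3 days for outpatients), not discharge. No section says that ventilation or ICU dates come from those records. This stands. Case A is then the likelier outcome, and its error is small.

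A reader might infer that the plan overstates ventilation risk by more than a standard error, and more so in the arm discharged sooner. The documents support neither. The first needs the censoring rule of Case B and timing that the documents do not give. The second holds with equal event hazards (0.37 against 0.44) but reverses on the absolute scale at 40% against 15% with median stays of 10 and 7 days (0.37 control, 0.27 ibrutinib). Moreover, the SE used above is that of a complete proportion. Under discharge censoring the estimate itself is noisier (simulated SD 16-17 points at mean time to ventilation of 4 days, 22-24 at 6 days), so the bias is a smaller multiple of its own SE.

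It is also fair that Section 13 plans only per-arm estimates here, with no test or decision rule. What the reply does not remove is death before the event: follow-up after discharge does not cure that, and Section 13 does not address it.

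**Conclusion.** The point holds as a minor one. Section 13 applies Kaplan-Meier to two endpoints for which death is a competing event, and leaves the handling of discharge open. With discharged patients kept at risk, the day-30 risk is overstated by about 0.1 to 3 points, under half an SE. That rests on 33 per arm, 20-25% ventilated, 5-20% dying first, and deaths not falling mostly before ventilations. If discharge were also a censoring date, the error could be anything from negligible to several SE, and could move the arm contrast either way. That is a reason to close the gap, not evidence that the plan commits the error.

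The figures model ventilation. The same reasoning applies to ICU admission, for which no separate size was computed. The primary Fisher test, the power and the interim rules are unaffected.

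**What to change.** Add to the Secondary Endpoints paragraph of Section 13 that time to mechanical ventilation and time to ICU admission will be estimated to day 30 in each arm by the Aalen-Johansen cumulative incidence with 95% CI. Death without the event is a competing event. Patients discharged alive stay in the risk set as event-free to day 30 unless a later event is reported, with status confirmed at the scheduled 1-month contact. Counting from registration would match the primary endpoint.

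The cost is one sentence, a standard estimator, and asking about readmission, ICU stay and ventilation at a contact that already takes medical history and adverse events. No extra visit is needed. With complete follow-up and no other censoring, the day-30 estimate equals the simple proportion with the event, which is easy to check.

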	
ibrutinib (Arm A) versus control population receiving standard (Arm B) therapy
 
 • To determine the proportion of patients with viral clearance at end of ibrutinib therapy, time of hospital discharge and follow up thereafter among patients treated with ibrutinib (Arm A) versus control (Arm B) treatment • To determine the time and proportion of patients who develop IgM and IgG levels toward SARS-CoV-2 treated with ibrutinib (Arm A) versus control treatment (Arm B) • To examine immune cell subsets for absolute number, activation, exhaustion markers, and presence of maturation arrest (NK cells) at baseline and over time among patients treated with ibrutinib (Arm A) versus control (Arm B) treatment • To examine T-cell repertoire over time among patients treated with ibrutinib (Arm A) versus control (Arm B) treatment • To determine the influence of epigenetic age, clonal hematopoiesis, and monoclonal B cell lymphocytosis (MBL on treatment outcome • To determine serial change in inflammatory markers as CRP, ferritin, D-Dimer and cytokines including IL6, IL1B, and TNF-alpha serum levels over time among patients treated with ibrutinib (Arm A) versus control (Arm B) treatment.
Trial Design	
This study is a Phase 2 randomized double-blinded trial using a group sequential design with a lead-in cohort to better define safety and tolerability of ibrutinib combined with standard therapies for COVID-19 in a high-risk cancer population. The lead-in cohort and randomized trial define two separate components of the study.
 
Safety Lead-in Cohort
 
This study will begin with a 12 patient lead-in component to establish safety and better characterize toxicity prior to the randomized component. For safety purposes, patients will be enrolled in cohorts of 3 for the first 6 patients, and patients will receive ibrutinib at a dose of 420 mg daily. Dose limiting toxicity (DLT) will be evaluated during the first 14 days of treatment.
 
DLT would be considered to be any of the following:
 
 • Grade 4 hematologic toxicity that persists for 3 or more days that is considered at least possibly related to ibrutinib.

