2.2 Secondary Objectives

- To determine time to clinical resolution of need for supplemental oxygen (i.e. maintenance of oxygen saturation of 93% or greater on room air with ambulation) or need for supplemental oxygen above baseline for those on home oxygen.
- To determine rate of ICU admission and length of ICU admission for patients treated with ibrutinib (Arm A) versus control population receiving standard therapy (Arm B)
- To determine rate of shock requiring vasopressor support for patients treated with ibrutinib (Arm A) versus control population receiving standard therapy (Arm B)
- To determine the rate of secondary infection (bacterial, fungal, viral) for patients treated with ibrutinib (Arm A) versus control population receiving standard therapy (Arm B)
- To determine the time to hospital discharge for patients treated with ibrutinib (Arm A) versus control population receiving standard therapy (Arm B)
- To determine grade 3 or higher toxicity observed in patients treated with ibrutinib (Arm A) versus control population receiving standard therapy (Arm B)
- To determine time to mechanical ventilation, the number of days of mechanical ventilation per patient and total observed in patients treated with ibrutinib (Arm A) versus control population receiving standard therapy (Arm B)
- To determine the overall survival at 3 and 12 months post-enrollment.

Exploratory Objectives

- To determine the time to defervescence (oral temperature<100.5 degrees F for a 48 hour time period) among patients treated with ibrutinib (Arm A) versus control population receiving standardtherapy (Arm B)
- To examine the impact of baseline clinical features (e.g. type of cancer, active therapy), duration of symptoms prior to admission and laboratory features (e.g. T cell count) on outcome for patients treated on this therapeutic study
- To determine the proportion of patients with viral clearance at end of ibrutinib therapy, time of hospital discharge and follow up thereafter among patients treated with ibrutinib (Arm A) versus control (Arm B) treatment
- To determine the time and proportion of patients who develop IgM and IgG levels toward SARS-CoV-2 treated with ibrutinib (Arm A) versus control treatment (Arm B)
- To examine immune cell subsets for absolute number, activation, exhaustion markers, and presence of maturation arrest (NK cells) at baseline and over time among patients treated with ibrutinib (Arm A) versus control (Arm B) treatment

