12. STUDY CALENDAR^A

	Screening	Cycle 1 Day 1 ^I	Cycle 2 Day 1 ^I	End of Treatment (day 14 + up to 3 days if outpatient)	1 month post enrollment ^J	2 months post enrollment ^J	3 months post enrollment ^J	6 months post enrollment ^J	12 months post enrollment ^J
Informed Consent	X								
Medical History	X		X		X	X	X	X	X
Concomitant Medications	X	X	X	X	X	X	X	X	X
Adverse Events	X	X	X	X	X	X ^K	X ^K	X ^K	X ^K
Physical Exam	X	X	X	X					
Vital Signs^B	X	X	X	X					
EKG^C	X	X	X	X					
CBC with differential	X	X	X	X	X	X	X	X	X
Serum Chemistry^D	X	X	X	X	X	X	X	X	X
PT/PTT/INR, D- dimer, fibrinogen, LDH	X	X	X	X	X				
Hepatitis B,C Screening^E	X								
CRP, ferritin, troponin	X	X (daily)	X (daily)	X	X				
IL6, IFNγ, TNF	X		X	X					
Serum or Urine Pregnancy Testing	X								
Flow cytometry (Immunome)	X		X	X					
Total serum IgG, IgA, and IgM	X			X		X	X	X	X
Nasopharyngeal SARS-CoV-2 PCR^F	X			X	X (if negative will stop)	X (if negative will stop)	X (if negative will stop)		X (if negative will stop further testing)

Ibrutinib for COVID 19

					Further testing)	Further testing)	Further testing)		
Peripheral Blood for Correlative Laboratory Studies⁶	X	X	X	X	X	X	X	X	X
Ibrutinib or placebo			X						

- A. All research coordinator contact (consent, adverse events, concomitant medications) will be either by phone or over videoconference. Physical examination will be performed by the inpatient treatment team and does not have to be study personnel. For study participants who are discharged prior to completing 14 days, no daily labs will be performed at the outpatient setting and C2D1 labs will be performed on the day of discharge. Study participants will follow institutional inpatients/outpatient isolation initiation and discontinuation measures.
- B. Should include Oxygen saturations and O2 requirement. Consider continuous cardiac monitoring, especially for patients receiving concomitant medications with cardiac effects
- C. Consider continuous cardiac monitoring, especially for patients receiving concomitant medications with cardiac effects. All patients receiving hydroxychloroquine will be placed on telemetry as part of our standard institutional practice guidelines.
- D. Includes chem 10 and liver function panel. Should consider doing chemistry panel and CBC daily.

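### Section 13 analyses viral clearance at hospital discharge, a time with no dedicated scheduled PCR, and names no proportion analysis for the listed endpoint of clearance at end of therapy

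*Combined protocol and SAP*

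**What the plan says.** The time points for viral clearance differ between parts of the document.

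- Section 13, under secondary endpoints, names one analysis of clearance: "The proportion of patients with viral clearance at the time of hospital discharge will be estimated", with a 95% confidence interval in each arm. It calls these analyses largely descriptive.
- Section 3.2 lists two secondary endpoints on clearance: "Viral clearance at the end of therapy" and "Time to viral clearance". It does not list clearance at discharge.
- The exploratory objective, in the synopsis and under Section 2.2, covers three times: "viral clearance at end of ibrutinib therapy, time of hospital discharge and follow up thereafter".
- The study calendar row "Nasopharyngeal SARS-CoV-2 PCR" is marked at screening, end of treatment and months 1, 2, 3 and 12. End of treatment is defined as "day 14 + up to 3 days if outpatient". There is no discharge column.
- Calendar footnote A moves the Cycle 2 Day 1 labs to the discharge day for patients who leave before completing 14 days. The PCR row has no Cycle 2 Day 1 mark.
- Section 11 includes Cycle 2 Day 1 and end of ibrutinib among its sampling times and names nasopharyngeal PCR as one use of the samples. Discharge is not one of its times, and its detailed assay table has no PCR row. It also says that discharged patients who do not yet meet the criteria for ending isolation will not have laboratory studies, and that this is not a deviation.

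**The concern.** The one proportion that Section 13 promises is taken at a time for which the calendar schedules no dedicated swab. The listed fixed-time endpoint, which does have a scheduled swab, has no named proportion analysis.

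The choice of time also matters for interpretation. Duration of hospitalization is a secondary endpoint that treatment may change, and death in hospital is part of the primary endpoint. A proportion measured at discharge therefore mixes clearance with length of stay, and Section 13 does not say how patients who are never discharged alive are counted. The rationale argues that ibrutinib should enhance, or at least not compromise, viral clearance. If the drug shortened stay, its arm would be swabbed earlier and could appear to clear virus less well for that reason alone.

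**Working it through.** **Step 1: set the time points side by side.**

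| Time point | Exploratory objective | Section 3.2 endpoint | Calendar PCR | Named in Section 13 |
|---|---|---|---|---|
| End of therapy | yes | yes | yes | no |
| Hospital discharge | yes | no | no dedicated swab | yes |
| Follow-up | yes | no | months 1, 2, 3, 12 | no |
| Time to clearance | no | yes | from the swabs above | not by name |

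**Step 2: who would have a swab at discharge?** Patients discharged near day 14 would have the end-of-treatment PCR. Some patients discharged earlier might have one if the Section 11 list (Cycle 2 Day 1, PCR) is combined with footnote A, but the calendar row does not show that swab. Discharge before day 14 is foreseen: Section 7.2 sends the remaining drug home with the patient. So the data at discharge would be partial, and which patients have a swab would depend on when they left.

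**Step 3: the effect of measuring at discharge.** The documents give no clearance rate and no length of stay, so there is no stated figure to reproduce. What follows is an illustration on assumed values. Both arms have the same constant-rate clearance curve with median M days, so the proportion cleared by day t is

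F(t) = 1 − 2^(−t/M).

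Only the discharge day differs between arms.

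| M (days) | Discharge days | Earlier arm | Later arm | False gap |
|---|---|---|---|---|
| 8 | 7 vs 10 | 1 − 2^(−7/8) = 45.5% | 1 − 2^(−10/8) = 58.0% | 12.5 points |
| 12 | 7 vs 10 | 1 − 2^(−7/12) = 33.3% | 1 − 2^(−10/12) = 43.9% | 10.6 points |
| 16 | 7 vs 10 | 1 − 2^(−7/16) = 26.2% | 1 − 2^(−10/16) = 35.2% | 9.0 points |
| 14 | 8 vs 12 | 1 − 2^(−8/14) = 32.7% | 1 − 2^(−12/14) = 44.8% | 12.1 points |

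These four cases are not a bound. With M = 8 and discharge on day 8 vs day 12, the values are 1 − 2^(−1) = 50.0% and 1 − 2^(−1.5) = 64.6%. With equal discharge days the gap is zero.

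**Step 4: the same curves at a common day 14.** F(14) is 70.3%, 55.5% and 45.5% for M = 8, 12 and 16, and 50.0% for M = 14. In each case the value is the same in both arms, so the gap is zero.

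**Step 5: scale.** The plan is 60 patients, or 66 with over-accrual, so 30 to 33 per arm. At a true proportion of 50% the 95% half-width for one arm is 1.96 × √(0.25/30) = 17.9 points, or 1.96 × √(0.25/33) = 17.1 points. The illustrated gaps are smaller than this sampling error. They are bias, however, so the interval does not account for them.

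**The case against.** The strongest reply has five parts.

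1. The exploratory objective names discharge, so Section 13 does analyse a stated time point. This stands. A reader might infer that the discharge analysis has no basis in the plan, and that would be wrong. The same objective also names end of therapy, which Section 13 leaves out.
2. A reader might infer that the discharge analysis would have no data at all. The documents do not support that. Patients leaving near day 14 have the scheduled PCR, and Section 11 with footnote A could yield discharge-day swabs for some others. What holds is that no PCR is dedicated to discharge, and that Section 11 and the calendar disagree.
3. Section 13 covers time-to-event endpoints by Kaplan-Meier with an open list and allows estimates at specific times. Section 11 promises descriptive comparisons of the correlative results. Time to clearance can be read into the first, and clearance in general into the second. Neither names the end-of-therapy proportion, so the gap is one of specification.
4. The size is hypothetical. A reader might take 9 to 12.5 points as the bias expected in this trial. It is not: the medians and discharge days are assumed, and the documents do not say which arm would leave sooner. No test of clearance is planned.
5. Moving to day 14 does not remove the dependence on discharge. Patients sent home and still under isolation may have no day-14 swab, and that may go with persistent virus. Counting them as not cleared could again penalise the arm discharged sooner. This stands, and the fix has to deal with it.

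**Conclusion.** The mismatch is established from the text alone. Section 13's only named clearance proportion is at discharge, where no PCR is dedicated. The listed and scheduled end-of-therapy endpoint has no named proportion analysis, and no rule is given for in-hospital deaths. The dependence on length of stay follows from the definition. Its size does not: about 9 to 12.5 points holds for four cases with identical constant-rate clearance, medians of 8 to 16 days and discharge 3 or 4 days apart. The effect of in-hospital deaths cannot be sized, because the design gives event rates only for respiratory failure or death combined.

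The consequence is limited. These are descriptive analyses, and the primary endpoint, sample size, interim rules and safety rules are untouched. The change is still worth making, because the plan already schedules the sample that a better-defined analysis needs.

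**What to change.** In Section 13:

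- Name the proportion cleared at end of therapy (day 14, plus up to 3 days for outpatients), per arm with a 95% confidence interval, as the clearance analysis. Use the scheduled PCR, all randomized patients as denominator, and deaths counted as not cleared.
- Add the 1-month PCR as a second fixed time. The calendar's rule of stopping tests after a negative result first appears at month 1, so that swab is still due in patients negative at end of treatment.
- Report the number of missing swabs by arm at each time. Show results twice: with missing counted as not cleared, and with observed swabs only. Both are needed because absence under the isolation rule may be related to clearance.
- Keep clearance at discharge, if at all, as an exploratory summary among patients with a swab, stating how many that is in each arm.

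Then reconcile the exploratory objective (synopsis and Section 2.2), Section 3.2, Section 11, the calendar with footnote A, and Section 13. This includes whether clearance is secondary or exploratory, and whether a PCR is due at Cycle 2 Day 1.

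The cost is wording in these sections, with no new samples or visits. If the sponsor wants discharge as a full analysis time, it would have to add a scheduled swab and state how deaths, patients still in hospital and missing swabs are handled.
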